2. INTRODUCTION

2.1. Background

Systemic lupus erythematosus (SLE) is a systemic chronic autoimmune disease characterized by autoantibody production, inflammation, and tissue damage in multiple organs. It is the prototypic systemic immune complex disease. It is highly prevalent in women and subjects of African descent. Clinical manifestations are protean and vary widely among subjects. They commonly include dermatitis (cutaneous lupus erythematosus [CLE]), arthritis, and nephritis, but the central nervous system and other major organ systems can also be affected.

Standard-of-care therapies used to treat SLE, such as antimalarials, steroids, and immunosuppressants, are only partially effective and have a wide range of toxicities. Durable remission is attained only in a minority of patients, the risk for flares and lupus nephritis (LN) activation and progression to end-stage renal disease is considerable, and the quality of life remains markedly reduced with work disability being very common. Achievement of low lupus disease activity status (LLDAS) is presently advocated as an important goal of the treatment of SLE. LLDAS achievement entails disease control (ie, low level of disease activity as in remission) with limited use of SOC antimalarials and steroids and no immunosuppressant. LLDAS is important, as it associates with the least likely development of long-term organ damage, either due to the disease or the therapies. Among the toxicities, those caused by steroids are of primary concern. Mortality stands out, which is due to cardiovascular disease and believed to result from the combined effect of steroids treatment with the course itself of SLE, which includes vasculitis. The antimalarials, however, also cause concerning toxicities. For example, hydroxychloroquine long-term use results in significantly impairing retinopathy, which has called to limit dosage as much as possible. Thus, there remains an unquestionable unmet medical need for more effective and safer therapies, above all those that, by specifically targeting critical molecules mediating SLE pathogenesis, may offer efficacy with mild or no unsafe consequences.

DS-7011a is an anti-Toll-like receptor 7 (TLR7) antagonistic monoclonal antibody (Mab) developed for the treatment of SLE. It is a humanized, double-mutation (Leu234Ala, Leu235Ala [LALA])-modified immunoglobulin (Ig) G1 that specifically binds to human and monkey (but not rodent) TLR7 and thus prevents TLR7 natural ligands from binding to and activating TLR7. Humanization decreases the potential for immunogenicity, while the LALA modification decreases the potential for cytotoxicity. In vitro, DS-7011a potently inhibits TLR7-mediated interleukin (IL)-6 production from human peripheral blood mononuclear cells. In mice, an anti-TLR7 Mab successfully treats several lupus models. In monkeys, DS-7011a shows general pharmacokinetic (PK) properties typical of an IgG1, permitting an administration frequency of once every 4 weeks (q4w), and shows no toxicities. Throughout all the toxicology studies, the maximum administered dose (400 mg/kg) was the no-observed-adverse-effect-level (NOAEL).

TLR7 is a nucleic acid sensor. Its natural ligands include exogenous (mainly from viruses) or endogenous (mainly from damaged cells) nucleic acids, especially those complexed with cationic peptides or antibodies. TLR7 ligation results in the production of interferon (IFN)-Type I and other cytokines like IL-6 by inflammatory cells and of antibodies by B-cells. TLR7 has been

extensively implicated in the pathogenesis of mouse lupus models and in SLE in humans, where it critically stimulates the production of inflammatory cytokines and autoantibodies. It may play a prominent role especially in SLE with active CLE and anti-Smith (Sm) and/or anti-ribonucleoprotein (RNP) autoantibodies. DS-7011a acts by binding to TLR7 and blocking its function, causing the inhibition of the production of multiple cytokines, including IFN-Type I, from multiple inflammatory cells, including the plasmacytoid dendritic cells (pDCs) and other inflammatory cells, such as B-cells and cells of the monocyte-macrophage lineage. In B-cells, TLR7 is also a critical mediator of antibody production in co-operation with the B-cell receptor. By blocking TLR7, DS-7011a may thus block critical mechanisms at the core of SLE pathogenesis and therefore be effective for the treatment of the disease.

2.2. Study Rationale

DS-7011a specifically binds to TLR7 and thus prevents TLR7 natural ligands from binding to and activating TLR7. By blocking TLR7, DS-7011a may block critical mechanisms, such as cytokine and autoantibodies production, at the core of SLE pathogenesis and therefore be effective for the treatment of the disease, which still represents an unmet medical need. This study will immediately follow DS-7011a first-in-human (FIH) Phase 1a study in healthy subjects and explore DS-7011a initial safety and efficacy in subjects with SLE to inform “go/no-go” decision to further development phases.

2.3. Dose Selection

DS-7011a will be administered intravenously (IV) 3 times at the dose of 20 mg/kg q4w. This dose was selected based on the safety, tolerability, PK, and pharmacodynamic (PD) results of the DS-7011a FIH Phase 1a study, which was a single ascending-dose study in healthy subjects in which DS-7011a was explored at the doses of 0.1, 0.3, 1, 3, 10, and 20 mg/kg. In said Phase 1a study, the 20 mg/kg dose was found to be similarly safe and well tolerated to lower doses but maximally active pharmacodynamically and thus selected to explore DS-7011a in subjects with SLE in this Phase 1b/2 study. According to preliminary analysis, in said Phase 1a study, the 20 mg/kg dose resulted after a single IV administration in extensive ex vivo inhibition of IL-6 production, which was of early onset and lasting duration and was still 86% on average, more than 65% in each subject, and more than 95% in 40% of subjects after 4 weeks from the administration. The 20 mg/kg dose, which is 1/6 of the NOAEL human equivalent dose, also resulted in C_{max} (719 $\mu\text{g/mL}$) and area under the plasma concentration time curve up to infinity (AUC_{inf}) (8838 $\text{day} \cdot \mu\text{g/mL}$) that didn't exceed monkey NOAEL (400 mg/kg) C_{max} (14,700 $\mu\text{g/mL}$ [female] or 13,800 $\mu\text{g/mL}$ [male]) and AUC_{inf} (29,300 $\text{day} \cdot \mu\text{g/mL}$ [female] or 34,200 $\text{day} \cdot \mu\text{g/mL}$ [male]).

2.4. Benefit and Risk Assessment

This Phase 1b/2 study will initially explore the safety, tolerability, PK, PD, immunogenicity, and efficacy of DS-7011a in subjects with SLE. It will immediately follow DS-7011a FIH Phase 1a study in healthy subjects and it will be conducted at the dose of 20 mg/kg (administered as single doses 3 times q4w [Weeks 0, 4, and 8]), which was found to be safe, well tolerated (according to preliminary analysis, it resulted in only one adverse event [AE] of constipation, mild and not drug-related), and maximally active pharmacodynamically in Phase 1a. DS-7011a is not

expected to cause concerning AEs, given the results of the toxicology studies and of Phase 1a study; however, given its mechanism of action, herpes zoster and respiratory tract infections, including COVID-19, will be monitored during this study as possible AEs of special interest (AESIs).

Pharmacology studies indicate DS-7011a may provide patients with SLE with a new targeted therapy positioned to considerably improve on current SOC. As described in the Investigator's Brochure (IB), DS-7011a demonstrated the ability to inhibit the TLR7-stimulated production of multiple cytokines from multiple cell types and the production of antibodies by isolated B-cells.

After initial work in healthy volunteers, DS-7011a will be administered to subjects with SLE 3 times at the dose of 20 mg/kg q4w IV, which is expected to be pharmacologically active based on pharmacology data obtained using a surrogate anti-TLR7 Mab in mice with a lupus model. This expectation has been confirmed by PD data obtained testing DS-7011a in healthy volunteers.

DS-7011a was safe and well tolerated in monkeys after the administration of multiple IV doses. In all studies, NOAEL corresponded to the maximum administered dose.

The data available on potential efficacy and toxicity permit the investigation of DS-7011a in SLE patients with a favorable benefit/risk ratio.

3. OBJECTIVES, HYPOTHESIS, AND ENDPOINTS

The objectives, definitions of associated endpoints as well as applicable outcome measures are described in [Table 3.1](#).

Table 3.1: Description of Objectives and Endpoints

Objectives	Endpoints	Category
Primary		
To explore the safety and tolerability of 3 doses of DS-7011a given IV every 4 weeks (q4w) in subjects with SLE.	Key safety parameters including, but not limited to: AEs, serious adverse events (SAEs), AESIs, such as herpes zoster and respiratory tract infections, including COVID-19, physical examination findings, vital sign recordings (body temperature, blood pressure, heart rate, respiratory rate), results of safety laboratory analyses of blood and urine, electrocardiogram (ECG) findings, and IgM, IgG, and IgA values, vaccine (diphtheria, tetanus, and pneumococcus) titers, and lymphocyte subset (cluster of differentiation [CD]3-, CD4-, CD8-, CD20-, CD16-, and CD56-positive) values.	Safety
Secondary		
To explore the PK properties of 3 doses of DS-7011a given IV q4w in subjects with SLE.	Key PK parameters including, but not limited to: area under the plasma concentration-time curve from time zero to time t (AUC_t), maximum plasma concentration (C_{max}), minimum plasma drug concentration (C_{min}), elimination half-life ($t_{1/2}$), apparent total body clearance of the drug from plasma (CL), apparent volume of distribution at steady state (V_{ss})	PK
To explore the clinical efficacy of 3 doses of DS-7011a given IV q4w in subjects with SLE	Several endpoints indicative of clinical efficacy including: Cutaneous Lupus Area and Severity Index Activity (CLASI-A), Cutaneous Lupus Activity Investigator Global Assessment (CLA-IGA), SLE Disease Activity Index 2000 (SLEDAI-2K), Physician's Global Assessment Systemic Lupus Erythematosus (PGA-SLE), Clinician's Global Impression of Change (CGI-C), Patient Reported Outcomes (PROs) such as quality of life assessments obtained using the Skindex-29+3	Efficacy

Objectives	Endpoints	Category
	and the Short Form 36 (SF-36) Questionnaires, Functional Assessment of Chronic Illness Therapy-Fatigue (FACIT-Fatigue), Itch Numeric Rating Scale (NRS), and Patient's Global Impression of Change (PGI-C), and laboratory parameters, such as autoantibodies (including antinuclear, anti-dsDNA, anti-Smith [Sm], and anti-ribonucleoprotein [RNP] antibodies), complement factors (C3, C4), erythrocyte sedimentation rate (ESR), and C-reactive protein (CRP).	
To explore the immunogenicity of 3 doses of DS-7011a given IV q4w in subjects with SLE.	Anti-drug antibodies (ADAs) against DS-7011a as the immunogenicity endpoint.	Immunogenicity
Exploratory		
To explore the mechanistic efficacy of 3 doses of DS-7011a given IV q4w in subjects with SLE.	Several endpoints indicative of mechanistic efficacy, including, but not limited to: circulating TLR7 and IFN-Type I gene signatures (GS); skin messenger ribonucleic acid (mRNA) coding for proteins under IFN-Type I regulation, such as myxovirus resistance protein (MxA), and for markers of inflammatory cells, such as CD45; and cytokines, including IL-6.	Pharmacodynamics (PD)

3.1. Rationale for Selection of Primary Endpoints and Key Secondary and Exploratory Endpoints

The main scope of this Phase 1b/2 study is to explore DS-7011a safety and tolerability as primary objectives, to explore efficacy, PK, and immunogenicity properties as secondary objectives, and to explore PD properties as exploratory objectives. The rationale for the selection of IgM, IgG, and IgA values, vaccine (diphtheria, tetanus, and pneumococcus) titers, and lymphocyte subset (CD3-, CD4-, CD8-, CD20-, CD16-, and CD56-positive) values should allow an initial insight into DS-7011a immunosuppressive potential. Regarding clinical efficacy endpoints, in addition to overall SLE parameters, the selection of parameters such as the Cutaneous Lupus Area and Severity Index Activity (CLASI-A), which are descriptive of CLE, should favor an initial detection of potential for beneficial clinical activity, given the expectation that TLR7 plays a particularly prominent role in the development of this component of the SLE disease. Regarding clinical laboratory efficacy and PD endpoints, the selection of biomarkers reflects their mechanistic proximity to TLR7 activation (TLR7 GS expression), TLR7 role in SLE pathogenesis (cytokines and autoantibody concentrations), and inflammatory effects that cytokines and autoantibodies have (complement factors and MxA and inflammatory cell marker mRNA). Anti-Sm and anti-RNP autoantibodies will be assessed with particular interest, since their production may especially depend on TLR7 and therefore be blocked by DS-7011a.

4. STUDY DESIGN

4.1. Overall Design

4.1.1. Overview

This Phase 1b/2 study will be double-blind, placebo-controlled, and randomized. It will be the second study in humans with DS-7011a, following an FIH study in healthy subjects. This study will explore the safety, PK, and proof of biological activity of DS-7011a in subjects with SLE, including active CLE. It will enroll up to 24 subjects with SLE in 2 parallel arms randomized to receive 2:1 DS-7011a or placebo. Tentatively, 9 of these 24 subjects will be of African descent. Since SLE appears to be particularly prevalent and difficult to treat in subjects of African descent, it will be interesting to see if DS-7011a may show initial evidence of efficacy in this population. Also, tentatively, 9 of these 24 subjects will be positive for anti-Sm and/or anti-RNP autoantibodies, since TLR7 may play a prominent role especially in SLE with anti-Sm and/or anti-RNP autoantibodies. This will be a multicenter study conducted at approximately 20 to 30 study sites in the US (mostly) and 2 to 4 other countries.

The study start date is the date when the first subject has signed informed consent. A subject is eligible to be enrolled into the interventional phase of the study when the investigator or designee has obtained written informed consent, has confirmed all eligibility criteria have been met by the subject, and all screening procedures have been completed.

Randomization will follow a randomization schedule generated by an independent biostatistician. Subjects, investigators, and site staff will be blinded, except for the unblinded site pharmacist or designee who will be responsible for preparing the study drugs. Sponsor's staff or representative (eg, clinical research organization) will also be blinded. If an unblinded clinical function representative is needed for any reason, firewall procedures will be followed to ensure blinding for the study remains intact.

The study will be divided into 3 periods: Screening, Treatment, and Follow-up. The Screening Period will be a maximum of 28 days. Rescreening is permitted during this phase after consultation with the Sponsor if the subject fails initial screening. Subjects will be randomized once considered eligible and will then enter the Treatment Period. Subjects will receive a dose of DS-7011a or placebo q4w 3 times. Dosing will be subordinate to a negative coronavirus disease 2019 (COVID-19) antigenic test, which will be performed on each study day of drug administration. Subjects will be followed until a final visit on Day 113 after the first study drug administration, when DS-7011a exposure and activity are expected to have declined. Additional extended follow-up will be conducted until Day 169 to monitor SAEs, AEs, and AESIs by telephone, unless there is the need to collect blood samples for anti-drug antibodies (ADA).

The subject population is described in Section 5. The overall study schema for this study is presented in [Figure 1.1](#).

4.1.2. End of the Study

The primary completion date is the date when the last subject is examined or receives an intervention for the purposes of final collection of data (database lock) for all outcome analyses (ie, the last subject's Final Visit [Day 113]). The global end of the study is the last subject's

Follow-up Visit (Day 169) (ie, the last subject's last visit overall). The study may be discontinued by the Sponsor for other reasons (ie, administrative, program-level or class-related), in which case the global end of the study would be the date the Sponsor discontinues the study.

The subject's End of Study (EOS) Visit is the date of their last study visit/contact. The scheduled EOS Visit on Day 169 will be by telephone unless there is the need to collect blood samples.

4.1.3. Dose Regimen

DS-7011a will be administered IV 3 times at the dose of 20 mg/kg q4w.

4.1.4. Duration

The study will be divided into 3 periods: Screening, Treatment, and Follow-up. The Screening Period will be a maximum of 28 days.

The study start date is the date when the first subject has signed informed consent. A subject is eligible to be enrolled into the interventional phase of the study when the investigator or designee has obtained written informed consent, has confirmed all eligibility criteria have been met by the subject, and all screening procedures have been completed. Overall study duration for a subject is expected to be up to approximately 28 weeks, which includes the 28-day Screening Period, Treatment, and Follow-up. A subject is expected to receive study drug for approximately 3 months (administered as single doses 3 times q4w [Weeks 0, 4, and 8]). Anticipated total duration of the study is approximately 15 months.

4.2. Rationale for Study Design

This Phase 1b/2 study is based on the hypothesis that DS-7011a will be safe and well tolerated and will show initial evidence of efficacy in adult subjects with SLE.

The rationale for running the study is presented in Section 2.2.

The rationale for the study design is to allow an unbiased and controlled interpretation of DS-7011a activity (safety, tolerability, and efficacy) based on the comparison of DS-7011a with placebo treatment, even if the sample size of this study was not calibrated to allow finding a statistically significant difference between DS-7011a- and placebo-treated subjects at pre-stipulated levels of probability and power. Blinding both investigators and study participants to treatment and randomizing assignment to treatment group is expected to avoid bias, while use of placebo provides control.

The rationale for three-month treatment duration is based on the expectation, given published results², that it is sufficient to explore DS-7011a initial safety and efficacy in SLE, namely, to impact the CLASI-A endpoint. According to cited results, three-month treatment duration was adequate time for an anti-BDCA2 antibody, which has a mechanism of action with similarities to DS-7011a, to show beneficial impact on CLASI-A and related pharmacodynamic biomarkers.

4.3. Justification for Dose Selection

DS-7011a will be administered IV 3 times at the dose of 20 mg/kg q4w. This dose was selected based on the safety, tolerability, PK, and PD results of the DS-7011a FIH Phase 1a study, which

was a single ascending-dose study in healthy subjects in which DS-7011a was explored at the doses of 0.1, 0.3, 1, 3, 10, and 20 mg/kg. In said Phase 1a study, the 20 mg/kg dose was found to be similarly safe and well tolerated to lower doses but maximally active pharmacodynamically and thus selected to explore DS-7011a in subjects with SLE in this Phase 1b/2 study. According to preliminary analysis, in said Phase 1a study, the 20 mg/kg dose resulted after a single IV administration in extensive ex vivo inhibition of IL-6 production, which was of early onset and lasting duration and was still 86% on average, more than 65% in each subject, and more than 95% in 40% of subjects after 4 weeks from the administration. The 20 mg/kg dose, which is 1/6 of the NOAEL human equivalent dose, also resulted in C_{max} (719 $\mu\text{g/mL}$) and AUC_{inf} (8838 $\text{day} \cdot \mu\text{g/mL}$) that didn't exceed monkey NOAEL (400 mg/kg) C_{max} (14,700 $\mu\text{g/mL}$ [female] or 13,800 $\mu\text{g/mL}$ [male]) and AUC_{inf} (29,300 $\text{day} \cdot \mu\text{g/mL}$ [female] or 34,200 $\text{day} \cdot \mu\text{g/mL}$ [male]).

The rationale for the use of placebo is the provision of treatment control, necessary to interpret DS-7011a activity (safety, tolerability, and efficacy), even if the sample size of this study was not calibrated to allow finding a statistically significant difference between DS-7011a- and placebo-treated subjects at pre-stipulated levels of probability and power.

5. STUDY POPULATION

Adult subjects (ages ≥ 18 years) with SLE including active CLE.

5.1. Inclusion Criteria

Subjects eligible for inclusion in this study have to meet all inclusion criteria for this study:

1. Male and female subjects must be of 18 years or more with definite SLE for at least 6 months prior to Screening, defined according to the 2019 European League Against Rheumatism (EULAR)/ American College of Rheumatology (ACR) classification criteria for SLE³, including documented history of positivity for antinuclear antibody (titer $\geq 1:80$).
2. Body mass index (BMI) ≥ 18 kg/m².
3. Presence of active CLE (acute, subacute, and chronic cutaneous lupus) with active skin involvement and a CLASI-A score of 4 or higher at the time of Screening and randomization, as recognized by 2 adjudicators, ie, the investigator in the periphery at the site and a centrally located arbiter contracted ad hoc (in case of disagreement between these 2 adjudicators, a third adjudicator, also centrally located and contracted ad hoc, will solve the disagreement and provide a final decision), despite adequate use of conventional therapies (either topical corticosteroids or antimalarial agents used for at least 12 weeks prior to Screening) or because of the requirement to discontinue these therapies due to side effects or poor tolerability.
4. Subjects must be willing to have skin tape harvests collected from the affected skin area (skin tape stripping done on the target lesion).
5. If the subject is a female of childbearing potential, she must have a negative serum pregnancy test at Screening and a negative urine pregnancy test at randomization, and she must be willing to use one method of highly effective birth control, as detailed in Section 10.2, and one barrier method, such as condom, diaphragm, or cervical cap with spermicide, upon enrollment, during the Treatment Period, and for 3 months following the last dose of study drug. A female is considered of childbearing potential following menarche and until reaching postmenopausal state, which is defined as no menstrual periods for a minimum of 12 months (a follicle-stimulating hormone [FSH] test may be conducted to confirm postmenopausal state according to investigator's discretion), unless made permanently sterile by surgery (undergone a hysterectomy, bilateral salpingectomy, or bilateral oophorectomy at least 1 month before the first dose).
6. If male, the subject must be surgically sterile or willing to practice birth control (Section 10.2) upon enrollment, during the Treatment Period, and for 3 months following the last dose of study drug.
7. Male subjects must not freeze or donate sperm starting at Screening and throughout the study period, and for at least 3 months after the final study drug administration.
8. Female subjects must not donate, or retrieve for their own use, ova from the time of Screening and throughout the study Treatment Period, and for at least 3 months after the final study drug administration.

9. Subjects must agree not to participate in any other investigational study during the study Treatment Period and for 3 months after the last dose of study drug.
10. Subjects must give written informed consent to participation in the study prior to Screening.
11. Subjects must be vaccinated against COVID-19.

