11. Treatment with SLE SOC medications, except for the following, which are allowed: oral prednisone (or equivalent at a maximum of 20 mg/d); antimalarials at SOC dose (maximum: hydroxychloroquine 400 mg/d, chloroquine 250 mg/d, quinacrine 100 mg/d); methotrexate (maximum 25 mg/wk); leflunomide (maximum 20 mg/d); mycophenolate (mycophenolate mofetil [MMF] maximum 3000 mg/d or mycophenolic acid sodium [MPS] maximum 2160 mg/d); azathioprine (maximum 200 mg/d); and tacrolimus (maximum 3 mg/d). These medications are allowed as long as they were initiated at least 12 weeks prior to randomization, have been stable for at least 4 weeks prior to randomization, and will remain stable for the duration of the study. Subjects who are not planning to continue these medications during the study must have discontinued them at least 4 weeks prior to randomization.
12. These medications are prohibited as follows:
 - Topical corticosteroids and other topical immunosuppressive agents, including topical calcineurin inhibitors, within 2 weeks prior to randomization (Day 1)
 - Intralesional corticosteroids, IV, intramuscular (IM), and intra-articular corticosteroids within 4 weeks prior to randomization (Day 1)
 - Cyclosporine, voclosporin, pimecrolimus, and sirolimus within 4 weeks prior to randomization (Day 1)
 - Cyclophosphamide within 24 weeks prior to randomization (Day 1)
 - IV Ig or plasmapheresis within 12 weeks prior to randomization (Day 1)
 - All biologic agents, including anti-B-cell antibodies (eg, rituximab, ocrelizumab, and belimumab), other antibodies (eg, anifrolumab, adalimumab, and tocilizumab), Fc constructs (eg, abatacept and etanercept), cytokines, and live vaccines within 12 weeks prior to randomization (Day 1)
13. History of suicide attempt or suicidal ideation within 1 year prior to Screening.
14. History of substance abuse within 6 months prior to Screening or a urine drug test at Screening resulting positive for amphetamines, barbiturates, benzodiazepines, cannabinoids, cocaine, and opiates. Medical marijuana may be used per discretion of the investigator.
15. History or positive test result for human immunodeficiency virus (HIV) at Screening.
16. Active hepatitis B virus (HBV) infection determined at Screening as positive test result for hepatitis B surface antigen.
17. Active hepatitis C virus (HCV) infection determined at Screening as HCV ribonucleic acid (RNA) above the limit of detection in subjects with positive HCV antibody titer.

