6.6. Prior and Concomitant Medications

All therapies received by subjects within 30 days prior to a subject's signing of the informed consent form (ICF) will be recorded as prior therapies.

All therapies used from the time the subject signs the ICF for study participation through the Follow-up Visits will be recorded as concomitant therapies. Concomitant therapies include all prescription, over-the-counter (OTC), and herbal remedies.

COVID-19 vaccine doses received prior to the study will be documented as prior medication, regardless of date of administration.

All prior and concomitant therapies will be recorded in the eCRF.

Changes to allowed (see Exclusion Criterion 11) SLE medications are permitted as long as they result in dose decrease and not increase.

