8.3. Medical History and Baseline Conditions

Subject's medical and medication histories (as detailed in Section 6.6) will be obtained by the investigator or a qualified designee.

Any untoward medical occurrence (including clinically significant laboratory values/vital signs that are out of range) that is noted prior to the dose of DS-7011a will be recorded.

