8.8.1.10. Pregnancy Testing

Women of childbearing potential who follow the contraception requirements of the study will be included in the study. A serum pregnancy test will be conducted on all females of childbearing potential at Screening so that results are available before enrollment. A urine pregnancy test will be conducted on all females of childbearing potential on Day 1, Day 29, Day 57, Day 85, and Day 113 (Final Visit) to rule out any change in status.

Women claiming postmenopausal status may have an FSH test conducted at Screening according to investigator's decision.

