10.2. Appendix 2: Highly Effective Contraception

Methods considered to be highly effective contraception include:⁴

- Combined (estrogen and progestogen containing) hormonal contraception associated with inhibition of ovulation:
 - Oral
 - Intravaginal
 - Transdermal
- Progestogen-only hormonal contraception associated with inhibition of ovulation:
 - Oral
 - Injectable
 - Implantable
- Intrauterine device
- Intrauterine hormone-releasing system
- Bilateral tubal occlusion
- Vasectomized partner
- Complete sexual abstinence

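### Criterion 5 counts 12 months without periods as menopause whatever the cause, so a woman who can still conceive can fall outside the contraception duty

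*Combined protocol and SAP*

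**What the plan says.** Section 5.1, criterion 5, gives two ways for a woman to leave the childbearing category. One is surgical sterility. The other is age-related in name but is defined by duration only: she is of childbearing potential "until reaching postmenopausal state, which is defined as no menstrual periods for a minimum of 12 months". The synopsis carries the same definition. An FSH test may be used as confirmation, at the investigator's discretion, and no cut-off is given. Section 8.8.1.10 repeats that the test is optional: "Women claiming postmenopausal status may have an FSH test conducted at Screening".

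Two sets of precautions depend on the classification.

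- **Contraception.** Criterion 5 requires a female of childbearing potential to use one highly effective method and one barrier method from enrollment until 3 months after the last dose.
- **Pregnancy tests.** Section 8.8.1.10 assigns the serum test at Screening to the same group, and likewise the later tests: "A urine pregnancy test will be conducted on all females of childbearing potential".

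The accepted contraceptive methods in Section 10.2 include hormonal ones, for example "Progestogen-only hormonal contraception associated with inhibition of ovulation". Exclusion criterion 12 bars cyclophosphamide only in the 24 weeks before Day 1, so earlier use is compatible with entry.

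**The concern.** A definition by duration alone does not separate menopause from other reasons for absent periods. Section 5 opens the study to adults from age 18, so the definition can apply to a woman of any adult age whose periods have been absent for a year. If the cause is reversible, the plan's own rule puts her in the wrong group.

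Safety is the primary objective. The background section describes the disease as especially common in women, and the earlier human study gave single doses to healthy subjects. Section 7.1 lists pregnancy among the reasons for stopping study drug, and Section 8.8.1.9 requires pregnancies to be reported whatever the woman's classification. Both provisions work only if the pregnancy is noticed. Criteria 5 to 8 show that the sponsor wants reproductive precautions during dosing and for 3 months afterwards, and the definition lets some women for whom they are meant fall outside them.

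**Working it through.** The plan gives no figure to reproduce. The check is a reading of every place that defines or uses the classification, followed by simple counts.

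**1. Does anything qualify the definition?** Criterion 5 and the synopsis have no cause clause and no age condition. FSH is optional in criterion 5, in the Table 1.1 footnote, in Section 8.4 and in Section 8.8.1.10, with no threshold and no stated consequence. Section 10.2 has no rule about absent periods during a hormonal method. Nothing elsewhere closes the gap.

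**2. Can an affected woman be enrolled?** Assumption (general clinical knowledge, not in the documents): hormonal contraception and cyclophosphamide can stop periods in a woman who can still conceive. Users of the hormonal methods in Section 10.2 are admitted, and so are women whose cyclophosphamide ended more than 24 weeks before Day 1. After 12 months without periods, either meets the literal definition of postmenopausal.

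**3. How long is the contraception duty that lapses?** Inputs: last infusion on Day 57 (Table 6.1) and 3 months after the last dose (criterion 5), taken as 91 days.

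- End of duty: Day 57 + 91 days = Day 148.
- Length from Day 1: 148 − 1 = 147 days; 147 / 7 = 21 weeks.

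**4. How many pregnancy tests are affected?** Scheduled tests: 1 serum (Screening) + 5 urine (Days 1, 29, 57, 85, 113) = 6. The protocol supports two readings for a woman classed as postmenopausal.

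| Text that the site follows | Limit stated | Tests not required |
|---|---|---|
| Section 8.8.1.10 | females of childbearing potential | up to 6 |
| Table 1.1, with Sections 8.1 and 8.4 | none on the pregnancy tests | 0 |

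No intermediate count has a textual basis. Table 1.1 gives the urine tests on Days 1, 29, 57, 85 and 113 in one row and the serum test in another, neither limited to a subgroup. A site that follows the table does all six.

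**5. How many women?** The documents give no frequency of absent periods, of hormonal method use or of earlier cyclophosphamide use among the up to 24 subjects. The number cannot be derived and may be zero.

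**The case against.** The strongest reply is that the practical loss is small. Several parts of it stand.

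- **Tests may not be lost at all.** Table 1.1 labels its FSH row for postmenopausal females but puts no such label on the pregnancy-test rows. Section 8.4 does the same for the serum test, and Section 8.1 lists both tests in the eligibility review without restriction. Section 8.8.1.10 says who will be tested, not that others will go untested. This stands, and it is why the count is 0 or up to 6 rather than 6. A reader might infer that a woman already pregnant on Day 1 would receive all three infusions unnoticed. That needs a misclassification, a pregnancy by Day 1 and a site that leaves out tests listed in its own schedule, and the text does not establish that chain.
- **A hormonal method protects.** This also stands. A reader might take the 21 weeks as unprotected time, but they measure a formal duty. What such a woman loses at once is the added barrier method and the obligation to continue her method.
- **The investigator will know the history.** Section 8.3 states that "medical and medication histories (as detailed in Section 6.6) will be obtained by the investigator", and Section 6.6 defines prior therapies as "All therapies received by subjects within 30 days prior to" consent. A reader might infer that earlier cyclophosphamide stays hidden. The documents do not support this: the history row of Table 1.1 names medications with no time window, and exclusion criterion 12 already forces an enquiry about cyclophosphamide over 24 weeks. Section 6.6 sets a recording category, not the limit of what a site may ask. Even so, knowing the history does not change the classification, because no rule ties the one to the other.
- **The word postmenopausal implies true menopause.** This does not stand. The sentence defines the term, and it does so by duration alone.

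**Conclusion.** The point holds as a defect in a stated rule, of modest and unquantified reach. Criterion 5 and the synopsis can class a woman with reversible absence of periods as postmenopausal. That removes a formal contraception duty of about 21 weeks and leaves it uncertain whether the six scheduled pregnancy tests are required of her.

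The conclusion rests on one assumption from outside the documents, that hormonal contraception or earlier cyclophosphamide can stop periods while a woman can still conceive, and on taking 3 months as 91 days. With 2:1 allocation, two in three such women would receive DS-7011a. A reader might infer a known risk to the fetus, but the documents state no fetal hazard. The finding is only that the protocol's own precautions, read literally, do not reach these women. A low-cost clarification is warranted.

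**What to change.** In criterion 5 and in the synopsis, define the postmenopausal state as at least 12 months without periods and without another medical cause, such as hormonal contraception or earlier cyclophosphamide. Add that a woman with another possible cause is treated as of childbearing potential unless the investigator documents menopause. Let Section 8.8.1.10 refer to that definition.

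Investigator judgement remains, but the default is reversed: at present 12 months settles the matter without any record of the reason, and under the change a doubtful case needs documentation. The change also settles the testing question for these women, since Section 8.8.1.10 and Table 1.1 would then both require the tests. Women whose menopause is documented are not burdened. Section 6.6 needs no new recording rule.

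The cost is a short text change in two places and a cross-reference in a third, with no new visit and no new type of test. The downside is a few extra urine or FSH tests and possibly a woman who declines the contraception requirement.
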